17.6. Immune-mediated adverse reactions

Immune-mediated adverse reactions occur in patients treated with pembrolizumab. Most adverse reactions are reversible and managed with interruptions of pembrolizumab, administration of corticosteroids and/or supportive care.

For suspected immune-mediated adverse reactions, ensure adequate evaluation to confirm aetiology or exclude other causes. Based on the severity of the reaction withhold pembrolizumab and administer corticosteroids as per guidelines in the table in section 17.16. Upon improvement to grade 1 or less, initiate corticosteroid taper and continue to taper over at least 1 month. Restart pembrolizumab if the adverse reaction remains grade 1 or less. If another episode of a severe adverse reaction occurs, permanently discontinue pembrolizumab.

Centres should monitor signs or symptoms that might indicate development of these adverse reactions and treat as per the guidance in section 17.16.

Treatment with pembrolizumab may increase the risk of solid organ transplant rejection. Patients who have had a solid organ transplant are excluded from c-TRAK TN.

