17.16. Pembrolizumab Dose Modification Guidelines for Drug-Related AE

General instructions:

- 1. Corticosteroid taper should be initiated upon AE improving to Grade 1 or less and continue to taper over at least 4 weeks.
- 2. For situations where pembrolizumab has been withheld, pembrolizumab can be resumed if AE has been reduced to Grade 1 or 0 and corticosteroid has been appropriately tapered to <10mg prednisolone (or equivalent) per day within 12 weeks of the last pembrolizumab infusion. Pembrolizumab should be permanently discontinued if AE does not resolve within 12 weeks of last dose or corticosteroids cannot be reduced to ≤10 mg prednisone or equivalent per day within 12 weeks.
- 3. Patients with a laboratory adverse event still at grade 2 after 12 weeks post last infusion may restart pembrolizumab if asymptomatic and only after consultation with the chief investigator.
- 4. For severe and life-threatening Immune Related AEs, IV corticosteroid should be initiated first followed by oral steroid. Other immunosuppressive treatment should be initiated if irAEs cannot be controlled by corticosteroids.

Immune-related AEs	Toxicity grade or conditions (CTCAE v4.0)	Action taken to pembrolizumab	Immune related AE management with corticosteroid and/or other therapies	Monitor and follow-up
Pneumonitis	Grade 2 Grade 3 or 4, or	Withhold Permanently	 Administer corticosteroids (initial dose of 1-2 mg/kg/day prednisone or equivalent) Administer additional anti-inflammatory managements as product 	 Monitor participants for signs and symptoms of pneumonitis Evaluate participants with suspected pneumonitis with radiographic imaging and initiate corticosteroid treatment
	recurrent Grade 2	discontinue	 inflammatory measures as needed. Add prophylactic antibiotics for opportunistic infections 	
Diarrhea / Colitis	Grade 2 (for > 3 days) or 3	Withhold	 Administer corticosteroids (initial dose of 1-2 mg/kg/day prednisone or equivalent) 	 Monitor participants for signs and symptoms of enterocolitis (i.e. diarrhoea, abdominal pain, blood or mucus in stool with or without fever) and of bowel perforation (i.e. peritoneal signs and ileus). Participants with ≥ Grade 2 diarrhea suspecting colitis should consider GI consultation and

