	Grade 4	Permanently discontinue		 performing endoscopy to rule out colitis. Participants with diarrhea/colitis should be advised to drink liberal quantities of clear fluids. If sufficient oral fluid intake is not feasible, fluid and electrolytes should be substituted via IV infusion
AST / ALT elevation or Increased bilirubin	Grade 2	Withhold	 Administer corticosteroids (initial dose of 0.5- 1 mg/kg/day prednisone or equivalent) 	 Monitor with liver function tests (consider weekly or more frequently) until liver enzyme value returned to baseline or is stable

ICR-CTSU

	Grade 3 or 4	Permanently discontinue	 Administer corticosteroids (initial dose of 1-2 mg/kg/day prednisone or equivalent) 	
Type 1 diabetes mellitus (T1DM) or Hyperglycemia	Newly onset T1DM or Grade 3 or 4 hyperglycemia associated with evidence of β-cell failure	Withhold until patient is clinically and metabolically stable	 Initiate insulin replacement therapy for participants with T1DM and for grade 3- 4 hyperglycemia associated with metabolic acidosis or ketonuria Administer anti-hyperglycemic in participants with hyperglycemia 	 Monitor participants for hyperglycemia or other signs and symptoms of diabetes. Evaluate patients with serum glucose and a metabolic panel, urine ketones, glycosylated hemoglobin, and C-peptide. For patients with grade 3 or 4 endocrinopathy that improves to grade 2 or less and is controlled with hormone replacement, continuation of pembrolizumab may be considered.
Hypophysitis	Grade 2	Withhold	 Administer corticosteroids and initiate hormonal replacements as clinically indicated. 	 Monitor for signs and symptoms of hypophysitis (including hypopituitarism and adrenal insufficiency)
	Grade 3 or 4	Withhold or permanently discontinue ^a	Therapy with pembrolizumab can be continued while endocrine replacement therapy is instituted	 Replacement of appropriate hormones may be required as the corticosteroid dose is tapered. For patients with grade 3 or 4 endocrinopathy that improves to grade 2 or less and is controlled with hormone replacement continuation of pembrolizumab may be considered.
Hyperthyroidism	Grade 3	Withhold	 Treat with non-selective beta-blockers (e.g., propranolol) or thionamides as appropriate 	 Monitor for signs and symptoms of thyroid disorders. Any grade 2 hyperthyroidism may also be treated

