	Grade 4	Discontinue ^a	 Replacement of appropriate hormones may be required as the corticosteroid dose is tapered. 	 Any grade 2 hyperthyroidism may also be treated as recommended. For patients with grade 3 or 4 endocrinopathy that improves to grade 2 or less and is controlled with hormone replacement continuation of pembrolizumab may be considered.
Hypothyroidism	Grade 2-4	Continue	 Initiate thyroid replacement hormones (e.g. levothyroxine or liothyroinine) per standard of care 	 Monitor for signs and symptoms of thyroid disorders. For patients with grade 3 or 4 endocrinopathy that improves to grade 2 or less and is controlled with hormone replacement continuation of pembrolizumab may be considered.
	Grade 2	Withhold		Monitor changes of renal function

ICR-CTSU

Nephritis ^b and Renal dysfunction	Grade 3 or 4	Permanently discontinue	Administer corticosteroids (prednisone 1-2 mg/kg/day or equivalent)	
Myocarditis	Grade 1 or 2	Withhold	Based on severity of AE administer corticosteroids	Ensure adequate evaluation to confirm etiology and/or exclude other causes
	Grade 3 or 4	Permanently discontinue		
	Grade 2	Withhold		Permanently discontinue if toxicity develops despite adequate premedication
Infusion Reaction ^c	Grade 3 or 4	Permanently discontinue		
Hepatitis	Grade 2 - 4	Withhold	 For grade 2, administer corticosteroids (prednisone 0.5-1mg/kg/day or equivalent) For grade 3 / 4, administer corticosteroids (prednisone 1-2 mg/kg/day or equivalent) 	Withhold or discontinue pembrolizumab based on severity of liver enzyme elevations.
Skin reactions including:	Grade 2 or 3	Withhold	 Administer corticosteroids (prednisone 1-2 mg/kg/day or equivalent) 	 Monitor patients for suspected severe skin reactions and exclude other causes.
 Dermatitis exfoliative Erythema multiform Exfoliative rash Bullous pemphigoid Stevens-Johnson syndrome grade ≥ 3 pruritus and rash (generalised or maculopapula r) 	Grade 4	Permanent discontinue		 Refer the patient to dermatology for assessment and treatment. If SJS or TEN is confirmed, permanently discontinue pembrolizumab.
All other immune- related AEs ^d	Intolerable/ persistent Grade 2	Withhold	 Based on type and severity of AE administer corticosteroids 	 Ensure adequate evaluation to confirm etiology and/or exclude other causes
May include:	Grade 3	Withhold or discontinue based on		• Pembrolizumab may only be restarted after grade 3 reactions following discussion with the ICR-CTSU.

|--|--|

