Note: Permanently discontinue pembrolizumab for any severe or grade 3 (grade 2 for pneumonitis) drug-related AE that recurs or any life-threatening event.

- a. Withholding or permanently discontinuing pembrolizumab is at the discretion of the investigator or treating physician.
- b. Renal function can be calculated using Serum creatinine OR estimated GFR (using Cockcroft-Gault).

c. For infusion reactions: if symptoms resolve within one hour of stopping drug infusion, the infusion may be restarted at 50% of the original infusion rate (e.g., from 100 mL/hr to 50 mL/hr). Otherwise dosing will be held until symptoms resolve and the patient should be pre-medicated for the next scheduled dose; Refer to Table 2 – Infusion Treatment Guidelines for further management details.

d. Patients with intolerable or persistent grade 2 drug-related AE may hold pembrolizumab at investigator's discretion. Permanently discontinue pembrolizumab for persistent grade 2 adverse reactions for which pembrolizumab has been on hold for ≥12 weeks.

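### Section 17.16 gives two different actions for a first, non-life-threatening grade 3 immune hepatitis, and nothing says which one decides whether pembrolizumab may be restarted

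*Protocol*

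**What the plan says.** Section 17.16 covers liver toxicity in two rows.

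- The row headed "AST / ALT elevation or Increased bilirubin" withholds at grade 2 and stops treatment permanently at grade 3 or 4.
- The Hepatitis row has a single action, withhold, for grades 2 to 4. It gives separate steroid doses for grade 2 and for grade 3/4. Its follow-up cell reads "Withhold or discontinue pembrolizumab based on severity of liver enzyme elevations".

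General instruction 2 of the same section applies after a withhold: "pembrolizumab can be resumed if AE has been reduced to Grade 1 or 0", provided steroids are tapered in time within 12 weeks of the last infusion. Section 17.6 has a similar rule: "Restart pembrolizumab if the adverse reaction remains grade 1 or less".

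Two texts require a permanent stop. Section 17.6 says "If another episode of a severe adverse reaction occurs, permanently discontinue pembrolizumab". The Note under the table says "Permanently discontinue pembrolizumab for any severe or grade 3 (grade 2 for pneumonitis) drug-related AE that recurs or any life-threatening event".

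Elsewhere the table marks where discretion or a central check applies. Footnote a, attached to hypophysitis and hyperthyroidism, says "Withholding or permanently discontinuing pembrolizumab is at the discretion of the investigator or treating physician". The row for all other immune-related events says "Pembrolizumab may only be restarted after grade 3 reactions following discussion with the ICR-CTSU".

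**The concern.** A patient with immune hepatitis and grade 3 AST/ALT or bilirubin fits both liver rows. One forbids any further pembrolizumab. The other only withholds it, and the general restart rules then come into play. The protocol does not say which row takes precedence.

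What is at stake is re-exposure after grade 3 liver toxicity. A site working from the Hepatitis row alone could restart once the event has settled and steroids are tapered, with no required discussion with the trials unit. A site working from the AST/ALT/bilirubin row could not restart at all. Both could cite section 17.16. Patients starting pembrolizumab here have no macroscopic disease on staging (section 3.2.1), so the restart rule should be unambiguous.

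**Working it through.** **Which text settles which case.** The case is a first, non-life-threatening grade 3 immune hepatitis with grade 3 AST/ALT or bilirubin.

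| Text | What it gives for this case |
|---|---|
| 17.16, AST/ALT/bilirubin row | Permanent stop |
| 17.16, Hepatitis row, action cell | Withhold |
| 17.16, Hepatitis row, follow-up cell | Either action, by enzyme severity; no grade, no row named, bilirubin not mentioned |
| 17.16, general instruction 2 | After a withhold, restart possible at grade 0-1 with steroids tapered |
| 17.6 | Restart after improvement; permanent stop only at another severe episode |
| 17.16, Note | Permanent stop for recurrent or life-threatening events; this case is neither |
| 17.16, footnote a | Not attached to either liver row |
| 17.16, row for all other events | Trials-unit discussion before restart after grade 3; hepatitis has its own row, so it is not covered |
| 17.12 | Refers back to 17.16 |
| 17.15 | Concerns toxicity unresolved at 12 weeks, not an event that recovers |

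At grade 2 the two liver rows agree (withhold). Recurrent grade 3 events, and grade 4 taken as life-threatening, are settled by the Note. The gap is therefore the first grade 3 event only. The Hepatitis row does cover that event, because it gives a grade 3/4 steroid dose.

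**How many patients.** Inputs:

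- Hepatitis of all grades: 0.7% (section 1.2.3).
- Numbers receiving pembrolizumab in the section 19.1.2 table: 24, 30 and 45. The top row has 68 ctDNA-positive patients. Under v6.0 all of these would be allocated treatment, but not all would start, since macroscopic disease on staging excludes them.
- Share of hepatitis that is grade 3: not given in the protocol. Assumed 0.25 to 0.75.

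Expected cases of any grade = 0.007 × n. Chance of at least one = 1 − 0.993^n. Expected grade 3 cases = 0.007 × n × share.

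| n treated | Expected, any grade | Chance of at least one | Expected grade 3 (share 0.25 to 0.75) |
|---|---|---|---|
| 24 | 0.168 | 15.5% | 0.042 to 0.126 |
| 30 | 0.210 | 19.0% | 0.053 to 0.158 |
| 45 | 0.315 | 27.1% | 0.079 to 0.236 |
| 68 | 0.476 | 38.0% | 0.119 to 0.357 |

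The any-grade figures are upper limits for the case in question, provided that the pooled 0.7% applies to this population. The one grade 3 hepatitis reported in the cited phase 1b trial in triple negative disease (section 1.2.3) shows that the event can occur but gives no usable rate.

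**The case against.** The strongest reply is that the two rows can be read together. The AST/ALT/bilirubin row is unconditional, and the patient's blood results meet it. The follow-up cell of the Hepatitis row points to enzyme severity, and the only graded enzyme rule in the table is that other row. Steroid doses match grade for grade, which suggests that the rows were meant to be used together. A site that stops permanently satisfies both rows, whereas one that restarts breaches one. General restart rules do not override a permanent-stop cell, here or for pneumonitis or nephritis. Such a case would also not go unseen: laboratory abnormalities of grade 2 or above are reported as adverse events (section 18.2), and serious events within 24 hours (section 18.3).

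Much of this stands. The stricter reading is plausible and is the safer one. But it is an inference. The follow-up cell names no row and no threshold, leaves both options open, and mentions enzymes only, so it does not reach bilirubin. The reading also does not explain why the action cell says withhold for grades 3 and 4 when other rows, such as pneumonitis, nephritis and myocarditis, state their permanent stops by grade. Event reporting informs the trials unit but does not control restart. The point that very few patients are involved is accepted.

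**Conclusion.** The concern holds. For a first, non-life-threatening grade 3 immune hepatitis with grade 3 AST/ALT or bilirubin, section 17.16 states two different actions, and no other text decides between them. The difference is confined to rechallenge.

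The size is small: fewer than one expected case in every scenario, and 0.04 to 0.24 first grade 3 cases in 24 to 45 treated patients if a quarter to three quarters of hepatitis is grade 3. That range rests on the pooled 0.7% and on an assumed grade split. It counts every grade 3 case as a first episode. The finding that the rows conflict rests on the text alone and does not depend on these figures. It is a patient-safety wording fault that should be fixed, with no bearing on sample size, primary endpoint or analysis.

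**What to change.** Give one action per grade for liver toxicity. Either split the Hepatitis row to match the AST/ALT/bilirubin row (withhold at grade 2, permanent stop at grade 3 or 4) or merge the two rows. In both cases delete the open-ended follow-up sentence or attach grades to it.

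If the clinical team wants rechallenge to remain possible after a first grade 3 hepatitis, write that as the single rule in both rows, with the trials-unit discussion that the row for all other immune-related events already requires.

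The cost is a wording change to one table row, or two if merged, which can go with the next amendment. Data collection, sample size and analysis do not change.

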17.17. Supply and distribution

Pembrolizumab is manufactured and provided free of charge by Merck, Sharp & Dohme to participating sites.

Mawdsleys will distribute pembrolizumab to participating sites.

No drug will be distributed to participating centres unless ICR-CTSU is satisfied that the required approvals and agreements and initiation procedures are complete.

17.18. Formulation, packaging, storage conditions and labelling

Pembrolizumab is provided as a liquid solution (100 mg/vial) in Type I glass vials, intended for single use only.

Pembrolizumab vials should be stored in original containers to protect from light exposure. The drug is stored as a liquid solution under refrigerated conditions (2 to 8 °C).

Please refer to the current approved pembrolizumab Investigator Brochure and the c-TRAK TN Pharmacy Guidance Notes for further information and guidance on the preparation, storage and stability of pembrolizumab within c-TRAK TN.

Merck Sharp & Dohme will label the pembrolizumab vials in accordance with the MHRA approved c-TRAK TN label. Pharmacies should add a dispensing label to the infusion bag at the time of reconstitution. Please refer to the Pharmacy c-TRAK TN Pharmacy Guidance Notes for more information.

17.19. Pharmacy responsibilities and drug accountability

The trial drug must not be used outside the context of the c-TRAK TN protocol.

Records must be kept of all deliveries, dispensing and destruction in accordance with the c-TRAK TN Pharmacy Guidance Notes. These records may be requested by ICR-CTSU during the trial to monitor supply and usage of stock. Account must be given of any discrepancies and certificates of delivery and return must be signed.

18. PHARMACOVIGILANCE

18.1. Definitions

18.1.1. Adverse Event (AE)

An AE is any untoward medical occurrence in a patient or clinical trial patient administered an investigational medicinal product; the event does not necessarily have a causal relationship with the treatment or usage.

18.1.2. Serious Adverse Event (SAE)

An SAE is any untoward medical occurrence that occurs after the commencement of trial treatment and within 90 days of the last administration or 30 days following cessation of treatment if the patient initiates new anti-cancer therapy, whichever is earlier, and:

- results in death,
- is life-threatening
- requires hospitalisation or prolongation of existing inpatients' hospitalisation
- results in persistent or significant disability or incapacity
- is a congenital anomaly or birth defect

Important adverse events that are not immediately life-threatening or do not result in death or hospitalisation but may jeopardise the patient or may require intervention to prevent one of the other outcomes listed in the definition above, may also be considered serious.

In addition, adverse events meeting either of the criteria listed below, are reportable to the ICR-CTSU in the same timeframe as SAEs to meet certain local requirements. Therefore, these events are considered serious by ICR-CTSU for collection purposes.

- Is a new cancer (that is not a condition of the study)
- Is associated with an overdose

Recurrence of the indicated disease and death due to recurrence of the indicated disease are not considered SAEs.

Pregnancy whilst participating in a trial is not itself considered an SAE but should be followed up for congenital anomalies or birth defects.

18.1.3. Serious Adverse Reaction (SAR)

A serious adverse reaction is an SAE that is suspected as having a causal relationship to the investigational medicinal product, as assessed by the investigator responsible for the care of the patient. A suspected causal relationship is defined as possibly, probably or definitely related (see definitions of causality table below).

Definitions of causality

Relationship	Description
Unrelated	There is no evidence of any causal relationship with the trial drug
Unlikely	There is little evidence to suggest there is a causal relationship (e.g. the event did not occur within a reasonable time after administration of the trial medication). There is another reasonable explanation for the event (e.g. the patient's clinical condition, other concomitant treatment)
Possible	There is some evidence to suggest a causal relationship (e.g. because the event occurs within a reasonable time after administration of the trial medication). However, the influence of other factors may have contributed to the event (e.g. the patient's clinical condition, other concomitant treatments)
Probable	There is evidence to suggest a causal relationship, and the influence of other factors is unlikely
Definitely	There is clear evidence to suggest a causal relationship, and other possible contributing factors can be ruled out
Not assessable	There is insufficient or incomplete evidence to make a clinical judgement of the causal relationship.

18.1.4. Suspected Unexpected Serious Adverse Reaction (SUSAR)

A serious adverse reaction, the nature or severity of which is not consistent with the reference safety information provided in the applicable Investigator's Brochure (IB), and is assessed as unexpected by the Chief Investigator.

18.1.5. Events of Clinical Interest (ECI)

Selected non-serious and serious adverse events are also known as Events of Clinical Interest (ECI) and must be reported within 24 hours to the ICR-CTSU.

Events of clinical interest for this trial include:

- 1. An overdose of pembrolizumab, as defined in section 17.14, that is not associated with clinical symptoms or abnormal laboratory results.
- 2. An elevated AST or ALT lab value that is ≥3 times the ULN and an elevated total bilirubin lab value that is ≥2 times the ULN and, at the same time, an alkaline phosphatase lab value that is ≥2 times the ULN, as determined by way of protocol-specified laboratory testing or unscheduled laboratory testing.*

*Note: These criteria are based upon available regulatory guidance documents. The purpose of the criteria is to specify a threshold of abnormal hepatic tests that may require an additional evaluation for an underlying aetiology.

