1.2.3. Pembrolizumab known benefits and risks

Pembrolizumab is generally well tolerated over a spectrum of tumour types and demonstrates a favourable safety profile in comparison to chemotherapy. Safety data from over 2700 patients has reported the most common adverse events of all grades were diarrhoea, cough, pruritis, arthralgia, rash, pyrexia and back pain (Pembrolizumab Investigator Brochure, Merck, Sharp & Dohme). Common grade 3-4 drug related adverse events were anaemia, raised alanine aminotransferase and aspartate aminotransferase.

Immune toxicities are well known among the immunotherapy drugs. Immune-mediated adverse reactions of all grades included hypothyroidism (8.4%), hyperthyroidism (3.4%), pneumonitis (3.4%), colitis (1.8%), severe skin reactions (1.4%), hepatitis (0.7%), hypophysitis (0.6%), diabetes mellitus (0.2%) and nephritis (0.1%). Other immune-mediated adverse reactions of clinical significance were reported in less than 1% of patients included uveitis, myositis, Guillian-Barre syndrome and pancreatitis. Events have been reported to occur from as early as the first dose to several months after the last dose of treatment and early recognition can allow initiation of symptomatic treatment preventing delays and discontinuation of treatment. Complications requiring steroids or immunosuppression are commonly reversible.

The first trial to report clinical activity of an immune check point inhibitor in TNBC was a phase 1b trial (KEYNOTE-012) showing that single agent pembrolizumab given at 10mg/kg IV once every 2 weeks (Q2W) was well tolerated and effective[26]. Twenty-seven heavily pre-treated recurrent or metastatic TNBC positive for PD-L1 were treated showing 18.5% of evaluable patients responded with one complete response, 4 partial

responses and 7 stable disease responses. Patients with a LDH greater than twice the upper limit of normal, which represents rapidly progressive disease had no response to pembrolizumab. Three patients remained on pembrolizumab for at least 11 months, which supports previous suggestions of the durability of pembrolizumab. Previous studies have mentioned the use of PD-L1 as a biomarker for response. However this study lacked correlation between the degree of PD-L1 positivity and response, questioning the use of PD-L1 as an appropriate biomarker [26].

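### The liver Event of Clinical Interest also requires ALP of at least 2 x ULN, so non-serious AST/ALT-plus-bilirubin elevations with lower ALP have no 24-hour reporting route

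*Protocol*

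**What the plan says.** Protocol section 18.1.5 lists the adverse events, serious or not, that "must be reported within 24 hours to the ICR-CTSU". The list has two items: an overdose without symptoms or abnormal laboratory results, and a liver criterion. The liver criterion has three parts:

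- "An elevated AST or ALT lab value that is ≥3 times the ULN";
- a bilirubin threshold, joined to the first part by a plain 'and': total bilirubin at or above twice ULN;
- a third requirement, for ALP, added with the words "and, at the same time, an alkaline phosphatase lab value that is ≥2 times the ULN".

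A note says the criteria come from regulatory guidance, which is neither named nor reproduced, and adds: "The purpose of the criteria is to specify a threshold of abnormal hepatic tests that may require an additional evaluation for an underlying aetiology".

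Four other places bear on this:

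- Section 1.2.3 states: "Common grade 3-4 drug related adverse events were anaemia, raised alanine aminotransferase and aspartate aminotransferase". It also lists hepatitis (0.7%) among the immune-mediated reactions.
- Section 17.16 has a row headed "AST / ALT elevation or Increased bilirubin" and a separate hepatitis row. Both act by grade or by severity of enzyme elevation. Neither mentions ALP.
- Sections 18.1.2 and 18.3 send every SAE to the trials unit within 24 hours, whatever the ALP. Important events that may jeopardise the patient or need intervention may also be considered serious.
- Section 18.2 has laboratory findings of grade 2 or above reported as adverse events on the CRF, with no 24-hour deadline.

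**The concern.** The ECI list adds little for serious events, because section 18.3 already gives them a 24-hour route. Its added value lies in events that nobody has classed as serious. For the liver, item 2 is the only laboratory-defined 24-hour trigger in the protocol.

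Because ALP is a required third condition, that trigger omits every patient with raised transaminase and raised bilirubin whose ALP is below 2 x ULN. The note says the threshold is there to pick out liver tests that may need a search for a cause. Nothing in the protocol explains why a combined AST/ALT and bilirubin elevation needs no such search when ALP is lower. An event that leads to permanent discontinuation under the AST/ALT or bilirubin row of section 17.16 can fall outside the liver ECI.

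What is at stake is how quickly the trials unit hears of a liver event, for a drug whose liver effects the protocol itself names as a risk.

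**Working it through.** There is no planned figure to reproduce. The check is of the rule's logic, followed by a rough size.

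**1. The rule.** Liver ECI = A and B and C, where A is AST or ALT at least 3 x ULN, B is total bilirubin at least 2 x ULN, and C is ALP at least 2 x ULN (section 18.1.5, item 2).

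**2. The rule applied to illustrative values** (assumed, in multiples of ULN; not from the protocol):

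| Case | ALT | Bilirubin | ALP | A | B | C | Liver ECI? |
|---|---|---|---|---|---|---|---|
| 1 | 10 | 4 | 1.2 | yes | yes | no | no |
| 2 | 10 | 4 | 2.5 | yes | yes | yes | yes |
| 3 | 3 | 2 | 2.5 | yes | yes | yes | yes |

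Cases 1 and 2 differ only in ALP. Case 3 has smaller transaminase and bilirubin elevations than case 1, yet it is reportable as an ECI and case 1 is not. Once C fails, no value of ALT or bilirubin can satisfy the rule.

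**3. Where case 1 goes instead.**

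- Judged serious (hospitalisation, life-threatening, or an important event in the investigator's judgement): 24-hour report under section 18.3. No gap.
- Not judged serious: an adverse event on the CRF under section 18.2, with no 24-hour deadline. This is the gap.

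**4. Comparison with section 17.16.** The AST/ALT or bilirubin row and the hepatitis row contain no ALP threshold. Clinical action in case 1 therefore does not depend on ALP, while ECI notification does.

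**5. Rough size.** Inputs: hepatitis of any grade 0.7% (section 1.2.3); 24, 30 or 45 patients on pembrolizumab (table in section 19.1.2). Section 19.1.2 also says that closing randomisation may raise the number treated; the table's highest scenario has 68 ctDNA-positive patients, so 68 is taken as an upper case.

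Expected cases = n x 0.007. Chance of at least one = 1 - 0.993^n.

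- n = 24: 24 x 0.007 = 0.17; 1 - 0.993^24 = 16%.
- n = 45: 45 x 0.007 = 0.32; 1 - 0.993^45 = 27%.
- n = 68: 68 x 0.007 = 0.48; 1 - 0.993^68 = 38%.

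These figures count hepatitis of any grade. Hepatitis cases that also meet A and B, have ALP below 2 x ULN and are not judged serious are fewer. Liver test elevations from other causes would add to the count, and the protocol gives no rate for them. The figures indicate scale only.

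**The case against.** The strongest reply is that little is lost. Serious liver events already go to the trials unit within 24 hours whatever the ALP. Liver tests are done before every cycle, grade 2 or higher findings are reported as adverse events, and the IDMC reviews safety at least annually. Management under section 17.16 does not wait for an ECI. That stands: the loss is speed of central notification for non-serious cases, not detection or treatment.

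It can also be said that sections 17.16 and 18.1.5 do different jobs and may have different thresholds. That stands too. The two sections are poorly aligned, but they do not strictly contradict each other. The conflict with the note's own stated purpose does not depend on section 17.16.

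A third reply is that the criterion rests on regulatory guidance not reproduced in the protocol. This limits what can be said about the intended wording. It does not change what the present wording does.

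A reader might go further and infer three things that the protocol does not support:

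- *That severe liver injury with normal ALP never gets 24-hour reporting.* Section 18.3 covers every case that is an SAE.
- *That normal ALP is the pattern to expect in immune hepatitis, or the more dangerous pattern.* Section 1.2.3 gives a frequency for hepatitis and describes no biochemical pattern. Section 17.8 lists raised ALP beside raised ALT and AST among the common reactions.
- *That the liver safety signal is inverted.* That would need a ranking of patterns by severity, which the protocol does not give.

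**Conclusion.** The point holds as a fault in a reporting threshold. As written, ALP of at least 2 x ULN is mandatory, so combined AST/ALT and bilirubin elevations with lower ALP are outside the liver ECI at any height. Those not judged serious have no 24-hour route to the trials unit. This works against the purpose stated in the note and sits badly with section 17.16.

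The logic is certain from the text. The practical size is small: on the protocol's own figures, roughly 0.2 to 0.5 hepatitis cases of any grade are expected among 24 to 68 treated patients, and only some of them would fall in the gap. Rarity does not justify a trigger that misses part of what it was set up to catch, and the correction is cheap.

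Two things remain open. The intended direction of the ALP inequality can be settled only from the guidance the note relies on. How many cases fall in the gap also depends on how readily investigators class a laboratory finding as serious. The point concerns reporting only and says nothing about how patients should be treated.

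**What to change.** Check the ALP condition, including the direction of its inequality, against the regulatory guidance behind the note in section 18.1.5, and name that guidance in the note. Then correct item 2 so that AST or ALT at least 3 x ULN with total bilirubin at least 2 x ULN is not excluded from 24-hour reporting because ALP is below 2 x ULN. The simplest way is to remove the ALP condition from this trigger.

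Reversing the inequality to ALP below 2 x ULN is not equivalent. It would stop reporting of cases with ALP at or above 2 x ULN, so it should be used only if the guidance calls for it.

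Reconcile item 2 with the liver rows of section 17.16, or state why the reporting threshold differs from the management one.

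The cost is one line in the protocol and matching wording on the ECI form. No new tests are needed, since ALT, AST, ALP and bilirubin are already measured before each cycle (sections 11.1 and 11.3). The downside is a few more 24-hour notifications.
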